## Appendix 6 Clinical Laboratory Tests

Laboratory Assessments	Parameters			
Hematology	Platelet count	Mean corpuscular volume (MCV)	Mean corpuscular hemoglobin (MCH)	White Blood Cell Count with Differential: 
 
• Neutrophils
 
• Lymphocytes
 
• Monocytes
 
• Eosinophils
 
• Basophils
 

	Hemoglobin			
	Hematocrit			
Coagulation	Prothrombin time	Activated partial thromboplastin time	International normalized ratio	
Biochemistry	Blood Urea Nitrogen	Potassium	Aspartate aminotransferase	Total bilirubin
	Urea a	Creatinine	Sodium	Alanine aminotransferase
	Glucose	Calcium	Alkaline phosphatase	Protein
	Total amylase	Lipase	Gamma-glutamyl transpeptidase	Albumin
	Magnesium	Serum cystatin C (for sites where the test is available)	Phosphorus	
Details of liver chemistry stopping criteria and required actions and follow-up assessments after liver stopping or monitoring event are given in Section 7.1.				
Routine Urinalysis	
 
• Specific gravity, physical appearance, color
 
• pH, glucose, protein, blood, ketones, bilirubin, urobilinogen, nitrite, leukocyte esterase by dipstick
 
• Microscopic examination (if blood or protein is abnormal)
 
			
Other Screening Tests	
 
• Follicle-stimulating hormone (FSH) and estradiol (as needed if not a woman of child bearing potential only)
 
• Serum or highly sensitive urine human chorionic gonadotropin (hCG) pregnancy test (as needed for a woman of child bearing potential).
 
• Serology (HIV antibody, hepatitis B surface antigen [HBsAg], and hepatitis C virus antibody)
 
• All of the safety labs will be performed locally
 
			

a Urea can be calculated using blood urea nitrogen (BUN), as follows:

If BUN is expressed in mmol/L then urea=BUN (factor = 1 for conversions in mmol (1 mole N2 = 2 moles N per mole of urea) then urea [mmol/L] = BUN [mmol/L])

If BUN is expressed in mg/dL it needs to be converted according to the following formula: urea [mg/dL] = BUN [mg/dL] × 2.1428. (conversion factor derived by: MW of urea = 60, MW of urea nitrogen = 14 × 2 => 60/28 = 2.1428)

If BUN is expressed in mmol/L and needs to be converted to urea mg/dL, the following formula must be used: urea (mg/dL) = BUN (mmol/L) × 0.357.

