15.4 Clinical Laboratory Evaluation

Laboratory assessments such as hematology and coagulation, biochemistry, urinalysis and other screening tests (e.g.: pregnancy tests) will be performed by local laboratories.

Laboratory results will be classified according to the NCI-CTCAE criteria version 5.0. Additional laboratory results that are not part of NCI-CTCAE will be presented according to the categories: below normal limit, within normal limits and above normal limit (according to the laboratory normal ranges).

The last measurement before study treatment first dose (including unscheduled measurements) will serve as the baseline measurement. For further details about baseline and change from baseline, please refer to Section 9.2.

Values below the detection limit will be imputed by half of the detection limit.

In case just a text value with an “> x” is reported it will be analyzed as +1 significant digit, e.g. “> 7.2 mmol” will be analyzed as 7.3.

Quantitative data will be summarized using descriptive statistics (n, mean, StDev, median, Q1, Q3, minimum, and maximum) of actual values and absolute changes from baseline to each scheduled visit over time. Scheduled visits performed during the safety run-in are to be presented, too.

Qualitative data based on reference ranges will be described according to the categories Low, Normal, and High (Hematology, Biochemistry and Coagulation). For qualitative data of urinalysis measurements, the raw classifications Normal, Trace/+, ++, +++, +++++ will be used instead. Results from the urinalysis microscopic examination (Erythrocytes, Leukocytes, Epithelial cells, Bacteria, Crystals and Casts) will only be listed.

Abnormalities classified according to NCI-CTCAE toxicity grading version 5.0 will be described using the worst on-treatment grade. Measurements from both scheduled and unscheduled visits should be considered for the worst on-treatment grade derivation; also measurements performed during the safety run-in are to be taken into account. For those parameters which are graded with two directions of toxicities such as potassium (hypokalemia/hyperkalemia), the toxicities will be summarized separately. Low direction toxicity (e.g., hypokalemia) grades at baseline and post baseline will be set to 0 when the variables are derived for summarizing high direction toxicity (e.g., hyperkalemia), and vice versa.

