- Concurrent (ALT or AST) $\geq 3 \times$ ULN and TBILI $\geq 2 \times$ ULN
- Concurrent (ALT or AST) $\geq 3 \times$ ULN and TBILI $\geq 2 \times$ ULN and ALP $> 2 \times$ ULN
- Concurrent (ALT or AST) $\geq 3 \times$ ULN and TBILI $\geq 2 \times$ ULN and ALP $\leq 2 \times$ ULN or missing

Concurrent measurements are those occurring on the same date.

Categories will be cumulative, i.e., a participant with an elevation of AST $\geq 10 \times$ ULN will also appear in the categories $\geq 5 \times$ ULN and $\geq 3 \times$ ULN.

Liver function elevation and possible Hy's Law cases will be summarized using frequency and percentage. An evaluation of Drug-Induced Serious Hepatotoxicity (eDISH) plot will also be created, with different symbols for different treatment groups, by graphically displaying

- peak serum ALT(/ULN) vs peak total bilirubin (/ULN) including reference lines at ALT = 3 \times ULN and total bilirubin = 2 \times ULN.
- peak serum AST(/ULN) vs peak total bilirubin (/ULN) including reference lines at AST = 3 \times ULN and total bilirubin = 2 \times ULN.

In addition, a listing of all TBILI, ALT, AST and ALP values for participants with a post-baseline TBILI $\geq 2 \times$ ULN, ALT $\geq 3 \times$ ULN or AST $\geq 3 \times$ ULN will be provided.

Estimated glomerular filtration rate (GFR [mL/min/1.73 m²]) will be derived using 4-component Modification of Diet in Renal Disease (MDRD) formula:

- GFR [mL/min/1.73 m²] = 175 \times serum creatinine (mg/dL)^{-1.154} \times age^{-0.203} \times 1.212 [if African American] \times 0.742 [if female]

In case only Urea or only Blood Urea Nitrogen (BUN) is collected for a participant at a specific visit conversion factors will be programmatically applied. Urea results will only be presented in listings.

Urea will be calculated using BUN, as follows:

- if BUN is expressed in mmol/L then
 - urea [mmol/L] = BUN [mmol/L]

and needs to be converted to urea [mg/dL] using the following formula:

- urea [mg/dL] = BUN [mmol/L] \times 0.357
- if BUN is expressed in mg/dL then:
 - urea [mg/dL] = BUN [mg/dL] \times 2.1428

Parameters with NCI-CTC grades available:

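### The factor 0.357 for deriving urea (mg/dL) from BUN (mmol/L) should be 6.0, which affects derived urea in listings only; separately, magnesium is on neither SAP Appendix 1 laboratory list

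*Protocol*

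**What the plan says.** **Urea.** Footnote a of Protocol Appendix 6 gives three rules for obtaining urea from BUN.

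- In mmol/L the two are equal (factor 1).
- In mg/dL, BUN is multiplied by 2.1428, justified by "MW of urea = 60, MW of urea nitrogen = 14 × 2 => 60/28 = 2.1428".
- From BUN in mmol/L to urea in mg/dL, the footnote states that if BUN "needs to be converted to urea mg/dL, the following formula must be used: urea (mg/dL) = BUN (mmol/L) × 0.357".

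SAP 15.4 carries the same three rules, to be applied by program when only urea or only BUN was collected at a visit. For BUN in mmol/L it sets urea equal in mmol/L, then adds "and needs to be converted to urea [mg/dL] using the following formula", followed by the factor 0.357. It also says: "Urea results will only be presented in listings".

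**Magnesium.** SAP 15.4 has two branches. The first is "Laboratory results will be classified according to the NCI-CTCAE criteria version 5.0". The next sentence sends results outside CTCAE to categories relative to the normal limits. The SAP then plans a worst on-treatment grade table and a shift table for each gradable parameter, with parallel worst-abnormality and shift tables for each non-gradable one. It points to Appendix 1 for the gradable list, and Appendix 1 also holds a non-gradable list. Magnesium is among the biochemistry tests in Protocol Appendix 6 but is on neither SAP list.

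**The concern.** The three urea rules cannot all be right. The first two fix what the third must be, and 0.357 is not that value. Protocol 8.2.4 asks local laboratories for normal ranges in SI units, so BUN in mmol/L is a foreseeable input. The SAP wording makes conversion to mg/dL look routine rather than optional. A program written to the plan would then list urea values that contradict the plan's own mg/dL rule for the same sample.

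The magnesium gap concerns a laboratory change that the protocol itself expects. Section 2.3 names hypomagnesemia among the very common cetuximab risks, and Section 6.5.4.1 describes progressive falls in serum magnesium. Every participant is planned to receive cetuximab. Protocol 9.4.2 plans graded laboratory results, with shift tables where applicable. If outputs are programmed from Appendix 1, no row is assured for magnesium in the tables that show how far it fell from baseline.

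**Working it through.** **1. Inputs (Protocol Appendix 6, footnote a).** Urea and BUN are equal in mmol/L; urea molecular weight 60; urea nitrogen 28 (14 × 2); stated factors 2.1428 (mg/dL to mg/dL) and 0.357 (mmol/L to mg/dL).

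**2. Reproducing the stated factors.**

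- mg/dL to mg/dL: 60/28 = 2.142857, printed as 2.1428. This reproduces.
- mmol/L to mg/dL: 1 mmol/L of urea = 60 mg/L = 60/10 = 6.0 mg/dL. The stated 0.357 does not reproduce.

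**3. Cross-check by the other route.** BUN in mmol/L × 28/10 = BUN in mg/dL, so the combined factor is 2.8 × 2.1428 = 5.9998, i.e. 6.0.

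**4. What 0.357 is.** 10/28 = 0.3571 converts urea nitrogen from mg/dL to mmol/L. That is a different conversion from the one described.

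**5. Size.** 6.0/0.357 = 16.8, and 0.357/6.0 = 0.0595, so the derived value is 5.95% of the correct one at every level.

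| BUN (mmol/L) | BUN (mg/dL) = × 2.8 | Urea via 2.1428 (mg/dL) | Urea via 6.0 (mg/dL) | Urea via 0.357 (mg/dL) |
|---|---|---|---|---|
| 2.5 | 7 | 15.0 | 15 | 0.89 |
| 5 | 14 | 30.0 | 30 | 1.79 |
| 10 | 28 | 60.0 | 60 | 3.57 |

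**6. Comparing the laboratory lists.** Protocol Appendix 6 names 19 biochemistry parameters. SAP Appendix 1 lists 13 as gradable and 3 as non-gradable (total protein, BUN, cystatin C), and 13 + 3 = 16. The 19 − 16 = 3 absent are:

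- urea, explained by the listings-only rule;
- phosphorus, possibly explained: SAP Section 4 cites protocol version 1.0, and the amendment log adds phosphorus later;
- magnesium, with no stated reason and no amendment entry adding it.

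**7. What still covers magnesium.** SAP 15.4 summarises quantitative data by descriptive statistics "of actual values and absolute changes from baseline to each scheduled visit over time", with no exclusion for magnesium. Low/Normal/High categories apply to biochemistry generally. Listings cover every laboratory parameter, flag out-of-range values and show CTCAE grades. Hypomagnesemia reported as an adverse event is graded and tabulated under SAP 15.2. What remains unsecured is the per-parameter worst-grade or worst-abnormality table and the baseline-to-worst shift table.

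**The case against.** The strongest case on the other side is that neither part changes a conclusion. For urea this largely stands. Measured urea, urea kept in mmol/L, and urea derived from BUN in mg/dL are all unaffected. BUN itself is on the non-gradable list and tabulated under its own name. The Protocol also makes the mixed-unit conversion conditional on need.

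A reader might infer that all listed urea is 16.8 times too small. The documents do not support that; only one of the three routes is wrong. A reader might also infer that BUN tables are contaminated, because SAP 15.4 mentions the case where only urea was collected. Neither document writes a urea-to-BUN formula, so no stated rule carries 0.357 into a tabulated value.

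For magnesium, a reader might infer that the SAP grades every laboratory result and that Appendix 1 contradicts this. That stops one sentence too early: results outside CTCAE go to normal-range categories. The documents do not reproduce CTCAE v5.0, so they do not show which branch magnesium falls under. It may also be said that Appendix 1 is not declared exhaustive, and that Protocol 9.4.2 promises shift tables only where applicable, without naming an analyte. These points limit the claim but do not remove it. Under either branch magnesium belongs on one of the two lists, and it is on neither.

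**Conclusion.** Both parts hold as minor corrections.

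The urea factor is wrong as written. The result rests only on constants printed in the Protocol and needs no outside source. Urea in mg/dL derived from BUN in mmol/L would be 16.8 times too small. The effect is confined to listings and arises only if such derivations occur, which depends on what local laboratories report.

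Magnesium is assigned to neither Appendix 1 list, and the protocol version gap that may explain phosphorus does not explain it. The consequence is limited to the worst-grade or worst-abnormality table and the shift table. It would not be right to say that magnesium goes unanalysed, or that a toxicity grade is necessarily lost. The study is descriptive with no hypothesis test, and no efficacy result or DLT assessment depends on either point.

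**What to change.** 1. In SAP 15.4, replace 0.357 with 6.0 for BUN (mmol/L) to urea (mg/dL). The program works from the SAP, so this alone corrects the listings.
2. Make the same change in Protocol Appendix 6 at the next amendment. Protocol Appendix 2 requires ethics approval of amendments, and this error does not justify one by itself.
3. In SAP Appendix 1, add magnesium and phosphorus to the gradable or the non-gradable list according to NCI-CTCAE v5.0, giving direction(s) of abnormality where gradable.

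The cost is one number in each document, two rows in SAP Appendix 1 and the matching table rows. No new data are needed.

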### AE/SAEs Observed in Association with Disease Progression

Progression of the disease/disorder being studied assessed by measurement of lesions on radiographs or other methods as well as associated clinical signs or symptoms (including laboratory abnormalities) will not be reported as AEs/SAEs, unless the participant's general condition is more severe than expected for the his/her condition and/or if the investigator considers that there is a reasonable possibility that the event was related to study intervention.

### Other Adverse Events to be Reported Using a Specialized Procedure or Form

- Overdoses (see Section 8.4) as described under "Reporting of SAEs" below.
- Pregnancies (see Section 8.3.5) as described under "Reporting of Pregnancies" below.
- DLTs (see Section 6.6.3) as described under "Reporting of DLTs" below.
- AESIs (see Section 8.3.7) as described under "Reporting of "AESIs" below.

### SAE Definition

If an event is not an AE per the definition above, then it cannot be an SAE even if serious conditions are met (e.g., hospitalization for signs/symptoms of the disease under study, death due to progression of disease).

A SAE is defined as any untoward medical occurrence that, at any dose:
a. Results in death
b. Is life-threatening
The term 'life-threatening' in the definition of 'serious' refers to an event in which the participant was at risk of death at the time of the event. It does not refer to an event, which hypothetically might have caused death, if it were more severe.
c. Requires inpatient hospitalization or prolongation of existing hospitalization 

• In general, hospitalization signifies that the participant has been detained (usually involving at least an overnight stay) at the hospital or emergency ward for observation and/or treatment that would not have been appropriate in the physician's office or outpatient setting. Complications that occur during hospitalization are AEs. If a complication prolongs hospitalization or fulfills any other serious criteria, the event is serious. When in doubt as to whether "hospitalization" occurred or was necessary, the AE will be considered serious.

• Hospitalization for elective treatment of a pre-existing condition that did not worsen from Baseline is not considered an AE.

• However, all events leading to unplanned hospitalizations or unplanned prolongation of an elective hospitalization (i.e., undesirable effects of any administered treatment) must be documented and reported as SAEs.

**A SAE is defined as any untoward medical occurrence that, at any dose:**

**d. Results in persistent disability/incapacity**

The term disability means a substantial disruption of a person's ability to conduct normal life functions.

This definition is not intended to include experiences of relatively minor medical significance such as uncomplicated headache, nausea, vomiting, diarrhea, influenza, and accidental trauma (e.g., sprained ankle) which may interfere with or prevent everyday life functions but do not constitute a substantial disruption.

**e. Is a congenital anomaly/birth defect**

**f. Other situations:**

- Medical or scientific judgment will be exercised in deciding whether SAE reporting is appropriate in other situations, such as important medical events that may not be immediately life-threatening or result in death or hospitalization but may jeopardize the participant or may require medical or surgical intervention to prevent one of the other outcomes listed in the above definition. These events are usually considered as serious.
  - Examples of such events include invasive or malignant cancers, intensive treatment in an emergency room or at home for allergic bronchospasm, blood dyscrasias or convulsions that do not result in hospitalization, or development of drug dependency or drug abuse.

**Recording and Follow-Up of AE and/or SAE**

**AE and SAE Recording**

- When an AE/SAE occurs, it is the responsibility of the Investigator to review all documentation (e.g., hospital progress notes, laboratory reports, and diagnostics reports) related to the event.
- The Investigator will then record all relevant AE/SAE information in the eCRF.
- As needed, the Sponsor or its designee may ask for copies of certain medical records (e.g., autopsy reports, supplemental lab reports, documents on medical history/concomitant medications, discharge letters), as supporting source documentation. All participant identifiers, except the participant number, will be redacted on these copies before submission to the Sponsor or its designee.
- The Investigator will attempt to establish a diagnosis of the event based on signs, symptoms, and/or other clinical information. Whenever possible, the diagnosis (not the individual signs/symptoms) will be documented as the AE/SAE.
- If an AE constitutes a DLT this is documented accordingly.
- Specific guidance is in the eCRF Completion and Monitoring Conventions.

### Assessment of Intensity

Investigators will reference the National Cancer Institute - Common Terminology Criteria for AEs (CTCAE), Version 5.0 (publication date: 27 Nov 2017), a descriptive terminology that can be used for AE reporting.

A general grading (severity/intensity; hereafter referred to as severity) scale is provided at the beginning of the above referenced document, and specific event grades are also provided.

If the severity for an AE is not specifically graded by NCI-CTCAE, the Investigator is to use the general NCI-CTCAE definitions of Grade 1 through Grade 5, using his or her best medical judgment.

The 5 general grades are:

- Grade 1 or Mild
- Grade 2 or Moderate
- Grade 3 or Severe
- Grade 4 or Life-threatening
- Grade 5 or Death

Any clinical AE with severity of Grade 4 or 5 must also be reported as an SAE. However, a laboratory abnormality of Grade 4, such as anemia or neutropenia, is considered serious only if the condition meets one of the serious criteria specified below.

If death occurs, the primary cause of death or event leading to death will be recorded and reported as an SAE. "Fatal" will be recorded as the outcome of this specific event and death will not be recorded as separate event. Only, if no cause of death can be reported (e.g., sudden death, unexplained death), the death per se might then be reported as an SAE.

### Assessment of Causality

- The Investigator will assess the relationship between study intervention and each AE/SAE occurrence:
  - Unrelated: Not reasonably related to the study intervention. AE could not medically (pharmacologically/clinically) be attributed to the study intervention. A reasonable alternative explanation will be available.
  - Related: Reasonably related to the study intervention. AE could medically (pharmacologically/clinically) be attributed to the study intervention.
  - A "reasonable possibility" of a relationship conveys that there are facts, evidence, and/or arguments to suggest a causal relationship, rather than a relationship cannot be ruled out.
- The Investigator will use clinical judgment to determine the relationship.

### Assessment of Causality

- Alternative causes, such as underlying disease(s), concomitant therapy, and other risk factors, as well as the temporal relationship of the event to study intervention administration will be considered and investigated.
- The Investigator will also consult the Investigator Brochure (IB) and/or Product Information, for marketed products, in his/her assessment.
- For each AE/SAE, the Investigator will document in the medical notes that he/she has reviewed the AE/SAE and assessed causality.
- There may be situations when an SAE has occurred, and the Investigator has minimal information to include in the initial report to the Sponsor or its designee. To meet the reporting timeline, the causality assessment is not required for the initial report.
- The Investigator may change his/her causality assessment after considering follow-up information and send a SAE follow-up report with the updated causality assessment.
- The causality assessment is one of the criteria used when determining regulatory reporting requirements.

### Follow-up of AEs and SAEs

- The Investigator will perform or arrange for the conduct of supplemental measurements and/or evaluations, as medically indicated or as requested by the Sponsor or its designee to elucidate the nature and/or causality of the AE or SAE, as fully as possible. This may include additional laboratory tests or investigations, histopathological examinations, or consultation with other health care professionals.
- If a participant dies during participation in the study or during a recognized follow-up period, the Investigator will provide the Sponsor or its designee with a copy of any post-mortem findings including histopathology.
- New or updated information will be recorded in the originally completed eCRF.
- The Investigator will submit any updated SAE data to the Sponsor or its designee within 24 hours of receipt of the information.

## Reporting of SAEs

### SAE Reporting by an Electronic Data Collection Tool

1. The primary mechanism for reporting an SAE to the Sponsor or its designee will be the electronic data collection tool.
2. If the electronic system is unavailable, then the site will use the paper SAE data collection tool, specified below, to report the event within 24 hours.
3. The site will enter the SAE data into the electronic system as soon as it becomes available.
4. After the study is completed at a site, the electronic data collection tool will be taken off-line to prevent the entry of new data or changes to existing data.
5. If a site receives a report of a new SAE from a study participant or receives updated data on a previously reported SAE after the electronic data collection tool has been taken off-line, then the site can report this information on a paper SAE form or to the Sponsor's safety department.
6. By exception, an SAE (or follow-up information) may be reported by telephone. The site will complete the electronic SAE data entry immediately thereafter.

